5. DEVICES USED IN THE STUDY

a. Investigational Devices (Including Commercial Devices Used Off-Label)

Investigational Device 1		
Name:	Nasal Airway Stent	
Description:	The Nasal Airway Stent (NAS) is inserted into the nose and serves as a	
	mechanical splint to prop open the upper airway.	
Significant Risk? (Y/N)	No	
Rationale for Non-Significant Risk	Device does not provide for any significant risk. The device is extremely soft and flexible and would be highly unlikely to cause any problems with the soft palate, throat, and/or upper airway.	

b. IDE-Exempt Devices

ND-Exempt Device 1	
Name:	NA
Description:	NA

6. DRUGS, BIOLOGICS, REAGENTS, OR CHEMICALS USED IN THE STUDY

a. Investigational Drugs, Biologics, Reagents, or Chemicals

Investigational Product 1	
Name:	NA
Dosage:	NA
Administration Route:	NA

b. Commercial Drugs, Biologics, Reagents, or Chemicals

Commercial Product 1		
Name:	NA	
Dosage:	NA	
Administration Route	NA	
New and different use? (Y/N)	NA	

7. DISINFECTION PROCEDURES FOR MEDICAL EQUIPMENT USED ON BOTH HUMANS AND ANIMALS

Not Applicable

8. **PARTICIPANT POPULATION**

a. Planned Enrollment

Our plan is to enroll 30 patients for the NAS study at Stanford. Stanford will be the only site. The population will be 18 years of age and older with snoring and obstructive sleep apnea and exclusion criteria of adults with body mass index (BMI) greater than 30 kg/m2.

b. Age, Gender, and Ethnic Background

Age range is 18 years and older. There are no gender or ethnic background specific criteria.

c. Vulnerable Populations

- No children will be asked to participate in the study.
- Pregnant women, homeless and economically disadvantaged people will be excluded.
- Persons who are not able to comprehend or understand English.
- Persons who are unable to follow instructions will be excluded.
- Persons with body mass index greater than 30 kg/m2 will be excluded.

d. Rationale for Exclusion of Certain Populations

No children will be included in the study, since standard-of-care treatment for sleep disorder management in children is less well defined and standardized than that of adults.

e. Stanford Populations

Laboratory personnel, employees, and/or students will not be excluded from the study, since they will be part of our normal clinic population. No specific number or share of laboratory personnel, employees, and/or students can be part of the study.

Those participants in this research study will also be eligible for the standard study cooperation fee of \$700 and the option of receiving nasal stents after their second sleep study.

Payments may only be made to U.S. citizens, legal resident aliens, and those who have a work eligible visa.

f. Healthy Volunteers

Not Applicable

g. Recruitment Details

Potential participants will be recruited from the Stanford Sleep Medicine Center clinic population as identified via chart review by the research staff. During their clinic visit, only someone with a treating relationship will initially approach the potential subject and, after they have indicated that they are interested in more information about the study, they will contact the research staff or agree to allow their physician to provide their contact information to the research personnel.

In addition, recruitment flyers will be posted in local businesses, as well as running a subject recruitment newspaper ad to obtain subjects outside of the Stanford Sleep Medicine Center clinic population. The phone number and email address of the research coordinator will be on the ads for the interested participant to contact.

h. Eligibility Criteria

i. Inclusion Criteria

The population under study will be clinical outpatients 18 years of age or older with symptoms of obstructive sleep apnea and snoring, and with body mass index less than 30 kg/m2.

ii. Exclusion Criteria

Children, pregnant women, homeless, economically disadvantaged individuals, and those who are unable to comprehend or understand English, or follow instructions will be excluded. Persons with body mass index greater than 30 kg/m2 will also be excluded.

i. Screening Procedures

Patients at age over 18 will be screened. Clinical outpatients will be recruited from our normal clinic population. No telephone screening will be performed. In addition, flyers will be posted to recruit subjects outside of our normal clinic population.

j. Participation in Multiple Protocols

Our research team will ask this question, and this question will be on our informed consent form. Patients will be given the choice as to whether they want to participate in this study if they are already enrolled in another study.

k. Payments to Participants

The patient will be paid to participate in this research study. It is a cooperation fee of \$700. The payments will be prorated based on the length of participation. Payments may only be made to U.S. citizens, legal resident aliens, and those who have a work eligible visa. Patients may need to provide their social security number to receive payment.

Participants will have the option to receive the nasal device after the second sleep study. The participant will be allowed to receive complimentary nasal stents until the time the device becomes commercially available.

I. Costs to Participants

There is no cost for participating in this study, other than basic expenses like transportation and the personal time it will take to come to all of the study visits. The study will pay for those services, supplies, procedures, and care associated with the study that are not a part of routine medical care. The patient will be responsible for any copayments and/or deductibles as required by your insurance.

m. Planned Duration of the Study

The consenting time will take about 15 minutes.

This research study is expected to last approximately one year. The active participation is up to a year. The time for the sleep questions will be about 30 minutes - the sleepiness scale will take about 5 minutes and the electronic questionnaire will take approx. 20 Min. The limit use of this device is a maximum of 10 hours - every night throughout the whole night for 7 days. At baseline and day 8 the patient will be requested to have sleep studies (without the NAS at baseline and while wearing the NAS at day 8).

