2. STUDY PROCEDURES

a. Procedures

This research study is seeking to enroll up to 30 participants with OSA and snoring. The enrollment will be at Stanford Sleep Medicine Center. The NAS (straight type) supports the soft palate from "collapsing" by supporting it physically, as well as securing the passage of airflow both inside and outside of the tube. Participants in the proposed study will undergo any or all of the following procedures.

After the consent process (30 min), each participant will be asked to complete either paper questionnaires which inquires about his or her demographic information and medical history (Sleep Disorders Questionnaire, 30 min) and level of daytime sleepiness in various situations (Epworth Sleepiness Scale, 5 min) or an electronic questionnaire (Alliance Sleep Questionnaire, 20 min).

Each participant will be asked to submit to an initial evaluation (60 min), which consists of a discussion of the participant's sleep habits and problems, medical history of participant and family, review of systems, medications, education, employment, and personal habits. A general physical examination, including but not limited to examination of the mouth and throat, and measurements of his or her weight and height; circumference of neck, waist, and hip; pulse and respiration rate; and blood pressure.

The participants will undergo two sleep studies: one sleep study at our center prior to using the NAS device (Baseline) and another after 7 days of use of the device at their

homes (Treatment). The participants will wear the NAS device during the second sleep study.

The sleep study will be conducted in routine fashion, with recording electrodes and equipment attached to the participant to enable monitoring of the electroencephalogram (EEG, C3-A2 and C4- A1, O2-A1 and O1-A2), electro-oculogram (EOG, ROC-A1, LOC-A2), chin and anterior tibialis electromyograms (EMG), heart rate by two-lead electrocardiogram (EKG), snoring intensity (anterior neck microphone), nasal pressure (nasal cannula), oral airflow(thermocouple), thoracic and abdominal movement (inductance plethysmography bands), and oxygen saturation (pulse oximetry). The duration of the application of all of these electrodes and recording devices to the participant is approximately 1.5 hours. The polysomnogram will be scheduled to allow at least 7 hours but no more than 9 hours of time in bed for the participant during the night.

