The Protocol Director will be monitoring all safety data from Stanford participants, and will determine if it remains safe for a subject to continue. A subject would be discontinued from the protocol at any time if it is determined that subject safety is at risk. The protocol director and/or study coordinator will be reachable by cell phone 24/7 by subjects.

Regarding an adverse/unexpected event, the lab personnel typically become aware of the event directly from the participant or the participant's healthcare provider. Upon becoming aware of an adverse event, the principal investigator should assess whether the adverse event represents an unanticipated problem:

1. unexpected;

2. related or possibly related to participation in the research; and

3. serious or otherwise one that suggests that the research places subjects or others at a greater risk of physical or psychological harm than was previously known or recognized.

e. Data Safety Monitoring Plan (DSMC)

i. Data and/or events subject to review

Data Collected From the Participant. Data from forms, questionnaires, and interviews will be entered into a secure, password-protected web portal. All data will also be collected and transferred in compliance with the Health Insurance Portability and Accountability Act (HIPAA).

ii. Person(s) responsible for Data and Safety Monitoring

The protocol director

iii. Frequency of DSMB meetings

Not Applicable

iv. Specific triggers or stopping rules

Within 24 hours of learning of a death, or within 5 days of learning of an unanticipated problem involving risks to participants or others.

v. DSMB Reporting

Not Applicable

vi. Will the Protocol Director be the only monitoring entity? (Y/N)

Not Applicable

vii. Will a board, committee, or safety monitor be responsible for study monitoring? (Y/N)

Not Applicable

f. Risks to Special Populations

Not Applicable

10. Benefits

Study participants will not receive direct benefit; however future sleep medicine patients may benefit. This information about NAS (nasal stent) appears to be a useful alternative or additive treatment for patients with OSA. We hope to gain through this study if this new device provides a better or alternative treatment of OSA.

11. **PRIVACY AND CONFIDENTIALITY**

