A Disposable Device NAS to Treat Obstructive Sleep Apnea and Snoring

NCT02928770

December 5, 2014

[name], PhD, Principal Investigator Stanford University Stanford, California 94305

Statistical Analysis Plan

The primary endpoint that will be evaluated in the study would be the AHI efficacy of the NAS device by PSG comparisons. The PSG factors concerned will be compared between the two PSG evaluations conducted, the initial control PSG evaluation without the NAS device applied and the PSG evaluation with the NAS device applied.

As for the questionnaires, each questionnaire such as the ESS, the BQ, the MQ, the SSS, the SAQLI and etc., obtained will be analyzed for determining qualitative factors regarding quality of life and sleep qualities. In addition, these questionnaires and interviews will be valuable resources regarding safety issues as well.

The secondary endpoint that will be evaluated in the study would be the safety of the NAS device. Interviews and questionnaires would be the mode of evaluation regarding the safety factors. The ultimate goal of safety would be finishing this clinical study without any adverse events or accidents that harm the subjects physically.

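### Section 8.e lets laboratory personnel enrol with no exception for the study team or the protocol director's subordinates, an avoidable conflict in harm and questionnaire reporting whose effect is unknown and probably small

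*Protocol*

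**What the plan says.** **Who may enrol.** Protocol 8.e: "Laboratory personnel, employees, and/or students will not be excluded from the study, since they will be part of our normal clinic population". The next sentence reads: "No specific number or share of laboratory personnel, employees, and/or students can be part of the study". The exclusion criteria in 8.h.ii begin: "Children, pregnant women, homeless, economically disadvantaged individuals, and those who are unable to comprehend or understand English, or follow instructions will be excluded". They then add a body mass index limit. Neither section mentions the study team or people who report to the protocol director.

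**How participants are found.** Under 8.g, clinic patients are first approached by someone with a treating relationship. The same section also provides for flyers and for "running a subject recruitment newspaper ad to obtain subjects outside of the Stanford Sleep Medicine Center clinic population". People who respond to these contact the research coordinator.

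**Design and outcomes.** Protocol 2.a describes one group with two sleep studies, the first without the device. Of the other it says: "The participants will wear the NAS device during the second sleep study". No masking is described. The SAP makes AHI by polysomnography (PSG) the primary endpoint. Safety is the secondary endpoint, evaluated by interview and questionnaire. Its stated aim is: "The ultimate goal of safety would be finishing this clinical study without any adverse events or accidents that harm the subjects physically".

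**Who handles harms.** Protocol 9.d says laboratory personnel typically learn of an event from the participant or the participant's healthcare provider, and the principal investigator then assesses it. It also says: "The Protocol Director will be monitoring all safety data from Stanford participants". Section 9.e names the protocol director as responsible for data and safety monitoring. It answers the items on board meetings, board reporting and a separate safety monitor as not applicable.

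**The concern.** Laboratory personnel appear in two roles: as eligible participants in 8.e and as the usual first recipients of adverse event reports in 9.d. Nothing keeps the two roles apart. A study-team member who enrolled would know when the device is worn, would give the harm and questionnaire answers personally, and could be giving them to immediate colleagues. The safety data would then be monitored by the protocol director, to whom that participant might report.

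Two things are at stake. The first is the credibility of the harm and questionnaire summaries, because these outcomes have no objective measurement behind them and no independent monitor is described. The second is voluntariness: a subordinate may find it harder to decline, complain or withdraw. The second point holds even if only one such person enrols.

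The reason given in 8.e, that staff belong to the normal clinic population, is also incomplete. It does not cover a staff member who answers a flyer or the newspaper ad. The treating-relationship safeguard in 8.g applies to the clinic visit and does not cover how outcomes and harms are collected.

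**Working it through.** **No stated figure to reproduce.** The planned enrolment is 30 (8.a: "Our plan is to enroll 30 patients for the NAS study at Stanford"). Neither document gives a sample-size calculation, an expected adverse event rate or an expected number of staff participants. The number 30 is not in dispute here.

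**Step 1: is the overlap permitted?** Section 8.e admits laboratory personnel, and 8.h.ii takes none of them out. The sentence in 8.e about a specific number or share most naturally means that no quota is set. Read literally it could mean that none may take part, but that would contradict the sentence before it. On the natural reading there is neither a cap nor a safeguard.

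**Step 2: is the overlap planned?** No. Staff must still be adults with symptoms of obstructive sleep apnea and snoring and meet the body mass index limit, so there may be few or none.

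**Step 3: how large could the effect on the harm rate be?** Let k of the 30 participants be staff who report no harms at all (the extreme case), and let p be the true share with a nosebleed or soreness. Both are assumptions.

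Observed rate = p × (30 − k) / 30. With p = 0.30:
- k = 0: 9/30 = 30%
- k = 3: 0.30 × 27/30 = 8.1/30 = 27%
- k = 6: 0.30 × 24/30 = 7.2/30 = 24%

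The relative loss is k/30 whatever p is: 3% for k = 1, 10% for k = 3, 20% for k = 6 and 33% for k = 10.

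For comparison, the 95% Wilson interval for 9/30 has centre (0.30 + 3.84/60) / (1 + 3.84/30) = 0.323 and half-width 1.96 × √(0.21/30 + 3.84/3600) / 1.128 = 0.156. It runs from about 17% to 48%. A shift of 3 to 6 percentage points lies well inside it.

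**Step 4: what about the aim of no adverse events?** The chance that at least one event is reported is 1 − (1 − p)^(30 − k), with p now the assumed true adverse event rate:

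| Assumed p | k = 0 | k = 3 | k = 6 | k = 10 |
|---|---|---|---|---|
| 5% | 0.785 | 0.750 | 0.708 | 0.642 |
| 10% | 0.958 | 0.942 | 0.920 | 0.878 |

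If no event is seen, the one-sided 95% upper bound on the rate is 1 − 0.05^(1/(30 − k)). This is 9.5% with 30 reliable reporters, 10.5% with 27 and 11.7% with 24.

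**Step 5: questionnaires.** If each staff participant overstated benefit by an assumed 2 points, the mean would shift by 2k/30: 0.07 points for k = 1, 0.20 for k = 3, 0.40 for k = 6 and 0.67 for k = 10.

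On all three measures the effect is small for one to three staff. It becomes material only if staff are a large share of the 30, which the protocol does not limit.

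**The case against.** The strongest reply is that 8.e is an open, deliberate eligibility choice, and that the main weakness lies elsewhere. Unmasked self-report, with safety monitored by the protocol director, affects all 30 participants. Removing a hypothetical few leaves that in place. This stands, and it is why the point is minor.

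A reader might infer more than the documents support:

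- **That staff who record or score the PSGs will take part, or that AHI is affected.** Neither document says who records or scores the PSGs, and neither defines laboratory personnel. No mechanism is shown by which a participant's job would change their AHI.
- **That staff would be reporting harms to their own superior.** No line-management structure is given. Reports typically reach laboratory personnel first and may come through a healthcare provider. The principal investigator then assesses them.
- **That the SAP's safety aim is a motive to under-report.** It can equally be read as a hope that nobody is harmed.
- **That the results are biased, or that a few staff would visibly change the adverse event rate.** Nothing shows that staff will enrol or under-report. Even complete silence from 3 to 6 of them is small against the precision of 30 participants.

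On voluntariness, the treating-relationship rule in 8.g is a partial safeguard for clinic patients. The consent form was not available for review, so missing wording for employees cannot be held against the plan.

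These points limit the size and certainty of the concern. They do not supply the missing exception in 8.h.ii or separate the two roles given to laboratory personnel in 8.e and 9.d.

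**Conclusion.** The point holds as a minor and inexpensive improvement. The protocol allows people involved in the study, or subordinate to the protocol director, to be participants. Harms and questionnaires are self-reported without described masking, laboratory personnel typically receive harm reports first, and no board is described. This could bias harm and questionnaire reporting and make participation or withdrawal less free for subordinates.

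The size is unknown and probably small. The move from 30% to 27% or 24% rests on three assumptions that the documents neither give nor rule out: a 30% true rate, 3 to 6 staff participants, and no harms reported by any of them. The direction, towards under-reporting, is also assumed. The primary AHI comparison and the planned 30 participants are not called into question. The voluntariness concern does not depend on this arithmetic.

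**What to change.** Amend 8.e and 8.h.ii to exclude:

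- members of the study team, including anyone who records or scores study PSGs or collects harm reports; and
- anyone who reports to the protocol director.

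State that other employees and students remain eligible. Reword the sentence in 8.e about a specific number or share so that it says plainly whether there is a limit.

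The cost is about one sentence in each of the two sections, the rewording in 8.e, and the loss of a few easily reached volunteers.

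If the investigator prefers not to exclude anyone, a weaker alternative is to record staff status at enrolment, have a person independent of the study collect harm reports from those participants, and repeat the safety and questionnaire summaries without them. This protects the reporting but does less for voluntariness.

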9. RISKS

a. Potential Risks

i. Investigational devices

If you insert the NAS into the nostril there can be a little nose bleeding because of the damage of the mucous membrane while inserting the NAS device.

There may be some soreness and swelling due to the pressure of the device.

ii. Investigational drugs

Not Applicable

iii. Commercially available drugs, biologics, reagents or chemicals

Commercially available drugs will be used as part of normal sleep disorder treatment. This is not a clinical trial to test medications, so routine medications for the treatment of sleep disorders will be prescribed by the subject's physician as part of their clinical care only.

iv. Procedures

Insertion of the NAS tube to the appropriate side of the nostril.

v. Radioisotopes/radiation-producing machines

Not Applicable

vi. Physical well-being

There can be a little nose bleeding because of the damage of the mucous membrane.

There may be some soreness and swelling due to the pressure of the device.

vii. Psychological well-being

No appreciable risks

viii. Economic well-being

No appreciable risks

ix. Social well-being

No appreciable risks

x. Overall evaluation of risk

Low - innocuous procedures such as phlebotomy, urine or stool collection, no therapeutic agent, or safe therapeutic agent such as the use of an FDA approved drug or device.

b. International Research Risk Procedures

Not Applicable

c. Procedures to Minimize Risk

This is a low-risk study, given that the participants will have procedures described above that are part of normal routine medical care.

Protections Against Risks

Treatment: We will have close monitoring of the participants while they are on treatment, including regularly scheduled visits to our center to maintain safety and adherence. Testing Information: We will keep all of the information collected about the participants in locked files at our center. For computerized data, the data will be stored in password-protected computers at our center.

Further, staff will have completed human subjects training.

d. Study Conclusion

The study will terminate when we have successfully enrolled 30 patients for the NAS study.

The Protocol Director will be monitoring all safety data from Stanford participants, and will determine if it remains safe for a subject to continue. A subject would be discontinued from the protocol at any time if it is determined that subject safety is at risk. The protocol director and/or study coordinator will be reachable by cell phone 24/7 by subjects.

Regarding an adverse/unexpected event, the lab personnel typically become aware of the event directly from the participant or the participant's healthcare provider. Upon becoming aware of an adverse event, the principal investigator should assess whether the adverse event represents an unanticipated problem:

1. unexpected;

2. related or possibly related to participation in the research; and

3. serious or otherwise one that suggests that the research places subjects or others at a greater risk of physical or psychological harm than was previously known or recognized.

e. Data Safety Monitoring Plan (DSMC)

i. Data and/or events subject to review

Data Collected From the Participant. Data from forms, questionnaires, and interviews will be entered into a secure, password-protected web portal. All data will also be collected and transferred in compliance with the Health Insurance Portability and Accountability Act (HIPAA).

ii. Person(s) responsible for Data and Safety Monitoring

The protocol director

iii. Frequency of DSMB meetings

Not Applicable

iv. Specific triggers or stopping rules

Within 24 hours of learning of a death, or within 5 days of learning of an unanticipated problem involving risks to participants or others.

v. DSMB Reporting

Not Applicable

vi. Will the Protocol Director be the only monitoring entity? (Y/N)

Not Applicable

vii. Will a board, committee, or safety monitor be responsible for study monitoring? (Y/N)

Not Applicable

f. Risks to Special Populations

Not Applicable

10. Benefits

Study participants will not receive direct benefit; however future sleep medicine patients may benefit. This information about NAS (nasal stent) appears to be a useful alternative or additive treatment for patients with OSA. We hope to gain through this study if this new device provides a better or alternative treatment of OSA.

11. **PRIVACY AND CONFIDENTIALITY**

All participant information and specimens are handled in compliance with the Health Insurance Portability and Accountability Act (HIPAA) and privacy policies of Stanford University, Stanford Health Care, and Stanford Children's Health.
